3. OBJECTIVES

3.1 Primary Efficacy Objective

Primary outcomes will be changes in LH, FSH, testosterone, estrogen, and quality of life from baseline, 14 weeks ± 7 days and 26 weeks ± 7 days.

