4.2 Duration of Study Participation

Total study duration will be 6 months and subjects will be provided with Natesto for the duration of the study (24 weeks treatment course).

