6. PATIENT SELECTION/ELIGIBILITY CRITERIA

6.1 Inclusion (Eligibility) Criteria

Subjects must meet the following criteria:

1. Voluntarily sign and date the study consent form(s) which have been approved by an Institutional Review Board (IRB). Written consent must be obtained prior to the initiation of any study procedures.
2. Male between 18 and 55 years of age, inclusive, with documented onset of hypogonadism prior to age 55.
3. Documented diagnosis of primary hypogonadism (congenital or acquired) or hypogonadotropic hypogonadism (congenital or acquired).
4. Serum total testosterone < 350 ng/dL based on 2 consecutive blood samples obtained 1-4 weeks apart between 6 and 10 AM following an appropriate washout of current androgen replacement therapy; with clinical symptoms of hypogonadism such as diminished energy and sexual function; and/or a decreased sperm count (<20 million sperm/mL semen).
5. Naïve to androgen replacement or has discontinued current treatment and completed a washout of 4 weeks following androgen treatment (excluding Testopel TM). Washout must be completed prior to collection of baseline serum testosterone samples to determine study eligibility.
6. Judged to be in good general health as determined by the principal investigator based upon the results of a medical history, physical examination, vital signs, and laboratory profile and a 12-lead electrocardiogram (ECG) performed at the time of enrolment of within the previous 6 months.

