7. STUDY DESIGN, CLINICAL, RADIOLOGICAL, LABORATORY AND SURGICAL EVALUATIONS

7.1 Study Design

This is a prospective clinical study aimed to evaluate the safety and efficacy of Natesto TM on patients with idiopathic hypogonadism. Clinical signs and symptoms of hypogonadism, i.e. diminished energy and sexual function; and/or a decreased sperm count constitute the clinical indication for TRT in our study population.

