7.3 Pre-Treatment Procedures and Evaluations

Upon evaluating the inclusion/exclusion criteria, patients will be recruited to the study. Patients will be instructed to stop any use of androgen replacement for 4 weeks prior to first treatment session and refrain from using any other androgen replacement therapy option during the study. After the washout period and before the first treatment session, patients will answer the IIEF-EF and SF-36 questionnaires for baseline evaluation.

7.4 Follow-Up Procedures and Evaluations:

Follow-up visits will be conducted at week 14+/- 7 days and 26+/- 7 days, these visits shall include:

- Measuring IIEF-EF and SF-36 scores of patients at the clinic
- Taking serum FSH, LH, E, and total Testosterone levels
- Semen analysis
- Reporting and recording adverse events at every follow-up visit.

Additional determinations of total serum testosterone will be performed periodically at every follow up visit, beginning one month after initiation of therapy. Additional semen analysis will be performed at weeks 15+/- 7 days and 27+/- 7 days.

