10. STATISTICAL CONSIDERATIONS

10.1 Primary Study Endpoints

The primary endpoint will be change in FSH, LH, Testosterone, and Semen Analysis after 6 months of treatment of Natesto.

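### Self-reported quality of life is a primary efficacy outcome in a study with no control or masking, so a gain from baseline cannot support an efficacy conclusion

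*Combined protocol and SAP*

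**What the plan says.** - **Primary status.** Section 3.1, under a heading that calls it an efficacy objective, states: "Primary outcomes will be changes in LH, FSH, testosterone, estrogen, and quality of life from baseline". Section 10.1 gives a different list: "The primary endpoint will be change in FSH, LH, Testosterone, and Semen Analysis after 6 months of treatment of Natesto". Change in "quality of life from baseline" is absent from the second list.
- **Design.** Section 7.1 describes a prospective study "aimed to evaluate the safety and efficacy of Natesto". Section 4.2 says "subjects will be provided with Natesto for the duration of the study". No section mentions a comparator, placebo, randomisation or blinding.
- **Instruments and timing.** The measures are IIEF-EF and SF-36. Section 7.3 states: "After the washout period and before the first treatment session, patients will answer the IIEF-EF and SF-36 questionnaires for baseline evaluation". The study calendar (section 12) instead marks the questionnaire at Visit 1, the week 1 screening visit at which consent is also taken, with first dispensing at week 2.
- **Population.** Section 6.1 item 4 admits men "with clinical symptoms of hypogonadism such as diminished energy and sexual function", joined by and/or to a low sperm count. Item 5 admits both androgen-naive men and men who have completed a 4-week washout. The expected split is not given.
- **Analysis.** Section 10.4 compares the two questionnaires between groups by Fisher's exact test, with significance at P<0.05. It mentions groups A and B, which are not defined anywhere.
- **Size.** The sample is 40 in section 4.1 and 80 in sections 6.3 and 10.3. No effect size, SD, expected non-drug response or power is stated.

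**The concern.** A change from baseline in a self-reported score is the sum of any drug effect and everything else that moves the score over six months. Two of the other components are expected here. Men who know they are taking an active treatment may report improvement because they expect it. Men who enter because of low energy or sexual function, the kind of complaint these forms record, will on average score somewhat better later even if nothing has changed. With no concurrent comparison, the plan cannot subtract either one.

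A third component affects only previously treated men. If their baseline form follows a washout, part of their gain may come from being on testosterone again. That is a pharmacological effect of Natesto, but not one particular to this product.

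Because 3.1 ranks quality of life with the hormones as a primary efficacy outcome, a P value below 0.05 invites the reading that Natesto improved quality of life. The design cannot support that reading, however small the P value.

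**Working it through.** **1. What can be reproduced.** Nothing. The heading of 10.4 announces a power calculation, but the section contains no power, effect size or SD. The figures below are an illustration on assumed inputs.

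**2. The test as written.** Fisher's exact test needs two independent groups and a categorical outcome. All men are to receive Natesto, groups A and B are undefined, and no cut-off is given for either questionnaire. The planned test therefore cannot be run as written. The outcome in 3.1 is change from baseline, so a within-subject test is the natural stand-in.

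**3. Inputs.**
- n = 80 (10.3) or 40 (4.1), with no dropout (assumed).
- Two-sided 0.05. The level is from 10.4; the sidedness is assumed.
- True drug effect zero; non-drug mean gain g = 0.2 or 0.3 SD of the score (assumed).
- Correlation r between baseline and follow-up of 0.5 to 0.8 (assumed).

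**4. Formula.** In units of the score SD, the standard error of the mean change is SE = sqrt(2(1 - r)/n). The paired t statistic is non-central t with n - 1 degrees of freedom and non-centrality g/SE. The probability of a significant improvement is the chance that it exceeds the 97.5% point of t (1.990 at n=80, 2.023 at n=40).

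**5. Results.**

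| n | r | SE | g/SE at 0.2 | P(significant) | g/SE at 0.3 | P(significant) |
|---|---|---|---|---|---|---|
| 80 | 0.5 | 0.112 | 1.79 | 0.424 | 2.68 | 0.755 |
| 80 | 0.6 | 0.100 | 2.00 | 0.506 | 3.00 | 0.842 |
| 80 | 0.8 | 0.071 | 2.83 | 0.798 | 4.24 | 0.987 |
| 40 | 0.5 | 0.158 | 1.26 | 0.234 | 1.90 | 0.456 |
| 40 | 0.6 | 0.141 | 1.41 | 0.281 | 2.12 | 0.543 |
| 40 | 0.8 | 0.100 | 2.00 | 0.496 | 3.00 | 0.833 |

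With no gain of any kind, the probability in this direction would be 0.025.

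**6. Sensitivity.**
- *Dropout.* With 20% loss from 80 (n=64) and r=0.6, SE = sqrt(0.8/64) = 0.112. A 0.2 SD gain then gives about 42%, against 51% without loss.
- *A Fisher-type reading.* Suppose scores are split at the baseline median, baseline and follow-up are treated as two independent groups, and r=0.5. By simulation, a 0.3 SD gain is significant in about 22% of trials at n=80 and 10% at n=40. The split and the grouping are assumptions too.

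**The case against.** The strongest case against has five parts.

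1. **The illustrated test is not the planned one.** This is correct. Under one workable version of the Fisher test, a modest non-drug gain would usually not reach significance. But a less sensitive test does not make a significant result attributable to the drug; it only makes one less frequent.

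2. **A reader might infer that most such trials would show a false gain.** The documents do not support that. They give neither the size of a non-drug gain nor the correlation. On the assumed values, 0.2 SD stays below one half at n=40 throughout, and at n=80 when r=0.5 (0.424).

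3. **A reader might infer that every man is symptomatic and has a baseline depressed by withdrawal.** Section 6.1 admits androgen-naive men, and its and/or wording leaves open whether a low sperm count can replace symptoms. The calendar also leaves unclear whether the baseline form follows washout. Moreover, improvement because Natesto restores testosterone is a drug effect, so it does not belong among gains that occur without one.

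4. **A reader might infer that only this outcome is affected.** Laboratory values resist expectation. But men are selected on testosterone below 350 ng/dL and may be selected on a low sperm count, so those outcomes are open to regression to the mean as well.

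5. **The plan commits to no quality-of-life claim.** Section 10.1 omits it and the hypotheses in section 2 concern sperm count only. That is fair, and it makes the change easier. But 3.1 still lists the outcome as primary and under efficacy.

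That there is a single unmasked cohort is itself an inference from what the protocol leaves out, and the mention of groups A and B sits badly with it. That conflict also needs resolving.

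**Conclusion.** The point holds in a limited form. As described, the study cannot attribute a change in IIEF-EF or SF-36 to Natesto, so quality of life should not be a primary efficacy outcome. This conclusion follows from the missing comparator and masking together with self-report, and does not depend on the arithmetic.

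The arithmetic shows only that the risk need not be small. For a 0.2 to 0.3 SD non-drug gain, a paired test would be significant in 42-99% of trials at n=80 and 23-83% at n=40. This assumes two-sided 0.05, no drug effect, r from 0.5 to 0.8 and no dropout. The range is wide because the protocol supplies none of the deciding quantities and gives two sample sizes.

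Two defects stand on the text alone: 3.1 and 10.1 disagree on whether quality of life is primary, and the questionnaire test in 10.4 has no defined groups.

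**What to change.** - **Section 3.1:** move quality of life out of the primary outcomes, which brings it into line with 10.1 on this outcome.
- **Section 10.4:** replace the between-group Fisher test for IIEF-EF and SF-36 with within-subject mean change from baseline and its 95% CI at weeks 14 and 26, labelled descriptive and uncontrolled. State that no efficacy conclusion will rest on these results. Define groups A and B or remove them.
- **Section 7.3 and the study calendar:** reconcile when the baseline questionnaires are completed relative to washout and first dispensing.

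These are wording changes. They add no arm, visit or data item. The real cost is giving up a questionnaire-based efficacy claim.

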3.2 Secondary Efficacy Objective

Secondary outcomes will be changes in sperm count from baseline, 14 weeks ± 7 days, and 26 weeks ± 7 days after treatment, as well as monitoring for adverse effects throughout the duration of our study.

4. STUDY DESIGN

4.1 Accrual goal

A total of 40 patients with a diagnosis of idiopathic hypogonadism (testosterone <350 on two consecutive T samples collected 1-4 weeks apart. meeting the eligibility criteria will be recruited from the Department of Urology clinic.

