6.3 Study Population

The study will consist of 80 males suffering from idiopathic hypogonadism.

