10.3 Sample size, accrual and study duration

TOTAL SAMPLE SIZE: 80
TOTAL ACCRUAL: 80
ACCRUAL DURATION: 6 months
STUDY DURATION: 27 weeks

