10.4 Statistical Analysis and Power calculation

The average and standard deviation of all relevant variables and baseline characteristics, primary and secondary outcomes will be calculated.

Change in sperm count will be analyzed using the ANOVA and MANOVA. A change in $< \pm 10\%$ will be reject the null hypothesis.

LH, FSH, E and Testosterone levels will be analyzed using one-sample t-test with repeated measures throughout the study.

IIEF-EF and SF-36 questionnaires will be analyzed and compared between the groups according to Fisher's exact test in each of the endpoints. The statistical significance will be set at $P < 0.05$.

Demographic characteristics such as age and testosterone level will be compared between groups A and B using student's test. Other demographic characteristics, such as medical background and risk factors will be compared between these groups using Fisher's exact test.

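### The sample size is given as 40 in Section 4.1 and as 80 in Sections 6.3 and 10.3, and nothing in the plan shows which governs

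*Combined protocol and SAP*

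**What the plan says.** Three sections of the combined protocol and SAP state how many men the trial will include.

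- Section 4.1 (Accrual goal): "A total of 40 patients with a diagnosis of idiopathic hypogonadism" who meet the eligibility criteria "will be recruited from the Department of Urology clinic".
- Section 6.3 (Study Population): "The study will consist of 80 males suffering from idiopathic hypogonadism".
- Section 10.3 (Sample size, accrual and study duration): "TOTAL SAMPLE SIZE: 80" and "TOTAL ACCRUAL: 80", with "ACCRUAL DURATION: 6 months".

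Section 10.4 carries the heading "Statistical Analysis and Power calculation". Its text lists descriptive statistics, tests and a 0.05 significance level. It gives no power, effect size, SD, dropout allowance or derived sample size.

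**The concern.** Sections 4.1 and 10.3 both claim to give total accrual, and they differ by a factor of two. Stopping at 40 falls short of Sections 6.3 and 10.3; continuing to 80 exceeds Section 4.1. The six-month accrual period in Section 10.3 sets a time limit, but it does not say whether recruitment ends once 40 men are in. The precision of every estimate depends on which figure is used, and without a derivation in Section 10.4 a reader cannot work back to the intended one.

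**Working it through.** **Comparison of the stated totals.** Section 4.1: 40. Section 6.3: 80. Section 10.3: 80 for sample size and 80 for accrual. The ratio is 80/40 = 2. There is no calculation in the plan to reproduce, so this is a conflict between statements and not a failed computation.

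**Could the two figures be reconciled?** We tried four readings.

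1. *40 per group.* Section 10.4 refers to comparisons between two lettered groups, but no section defines groups, an allocation or a control. Section 4.2 says "subjects will be provided with Natesto for the duration of the study" without separating groups, the study calendar in Section 12 has one schedule, and Section 4.1 calls 40 a total.
2. *40 per clinic.* Section 4.1 names the Urology clinic and Section 6.4 adds the Fertility Center, but no section divides the number by site.
3. *40 evaluable out of 80.* This needs dropout of 1 − 40/80 = 50%. No dropout rate is given, Section 4.1 calls 40 the accrual goal, and Section 10.3 sets sample size equal to accrual.
4. *80 consented, 40 enrolled.* Section 5.1 does separate study entry (consent) from enrollment (eligibility confirmed), and Section 4.1 counts eligible men. But no section attaches the 80 to consent: Section 6.3 makes it the study population and Section 10.3 the sample size.

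None is supported by the text.

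**What the choice is worth.** Our assumptions: one group, one-sample t-test on a within-man change, two-sided 0.05, no multiplicity adjustment. Only the 0.05 comes from the plan (Section 10.4), which does not state sidedness.

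- Ratio of standard errors: √(80/40) = 1.41.
- 95% confidence interval half-width, in SDs of the change: t(0.975, n−1)/√n. For n = 40, 2.0227/√40 = 0.320. For n = 80, 1.9905/√80 = 0.223.
- Smallest detectable mean change: the value of d at which the noncentral t distribution, with n−1 degrees of freedom and noncentrality d√n, gives 80% power.

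| Men with data | Half-width (SD) | Detectable change (SD) |
|---|---|---|
| 40 | 0.320 | 0.454 |
| 80 | 0.223 | 0.317 |
| 32 (40 less an assumed 20%) | 0.361 | 0.511 |
| 64 (80 less an assumed 20%) | 0.250 | 0.356 |

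The dropout rows assume that men without follow-up contribute nothing to the estimate.

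Power for three true mean changes:

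| True change (SD) | n = 40 | n = 80 |
|---|---|---|
| 0.317 | 50% | 80% |
| 0.5 | 87% | 99% |
| 0.6 | 96% | about 100% |

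**Sperm-count margin.** Section 2 frames the hypothesis as a change within ±10% of baseline. As an illustration, take two one-sided tests at 0.05 each, a true change of zero and a normal approximation. Power is then 2Φ(10/(SD/√n) − 1.645) − 1, with zero used where this is negative. With SD = 30 points: n = 40 gives 2Φ(2.108 − 1.645) − 1 = 36%; n = 80 gives 2Φ(2.981 − 1.645) − 1 = 82%.

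| Assumed SD of percent change (points) | n = 40 | n = 80 |
|---|---|---|
| 20 | 87% | 99.5% |
| 25 | 62% | 95% |
| 30 | 36% | 82% |
| 40 | 0% | 45% |

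The plan gives no SD, so this range is assumed.

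**The case against.** The best defence is that 80 is plainly meant. It appears in the section devoted to sample size, stated twice, and Section 6.3 agrees; Section 4.1 alone differs and may hold a figure that was never updated. That is plausible, and it is why we call the target inconsistent and not absent. But the documents do not establish it: Section 4.1 is itself headed as the accrual goal, and a majority of sections is no substitute for a derivation.

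A second objection is that no loss of power on a named endpoint has been shown. This stands. The contrast of 80% with 50% arises because 0.317 SD was picked as the change detectable with 80 men; at 0.5 or 0.6 SD both sizes do well. The t-test figures also would not describe a comparison between two groups, if one was intended.

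Third, the missing power calculation is a separate matter from the conflict: either could be repaired without the other. That is fair. The gap matters here only because it leaves nothing to settle which number applies, and it adds no weight to the severity.

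Finally, Section 9 has the investigators reviewing responses as they accrue, but the only stop to enrollment it mentions is for safety. We make no claim that results would decide when recruitment ends.

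**Conclusion.** The concern holds and must be fixed. The contradiction follows from the text alone and needs no assumption: a total of 40 in one operative section, 80 in two others, and no support for any reading that joins them. Its effect on precision is a factor of 1.41 in standard errors. How much that matters for a given endpoint cannot be said from the documents: for the sperm-count margin, the choice could be minor with an SD near 20 points or decisive with an SD near 30.

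**What to change.** State one number in Sections 4.1, 6.3 and 10.3, and say that it counts men enrolled in the sense of Section 5.1. If 40 was meant as a sub-total by clinic or by group, say so in Section 4.1 and define the split.

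It would also help, as a secondary matter, to give the basis for the chosen number under the Section 10.4 heading: a power calculation or the expected precision, naming the outcome and the assumed SD and dropout.

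The required change is wording only. It does not in itself call for more men: if recruitment is working to 40 and the sponsor confirms 80, men are added; if the sponsor keeps 40, it accepts the lower precision shown above.

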4.2 Duration of Study Participation

Total study duration will be 6 months and subjects will be provided with Natesto for the duration of the study (24 weeks treatment course).

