12. STUDY CALENDAR

| Visit #, Time | Visit 1 (Week 1) Screening | Visit 2 (Week 2) | Visit 3 (Week 6) | Visit 4 (Week 14) | Visit 5 (Week 15) | Visit 6 (Week 26) | Visit 7 (Week 27) |
|--------------------------------------|-------------------------------|---------------------|---------------------|----------------------|----------------------|----------------------|----------------------|
| Medical & Urological History | • | | | | | | |
| Physical Examination & Questionnaire | • | | | • | | • | |
| Informed Consent | • | | | | | | |
| Inclusion & Exclusion Criteria | • | | | | | | |
| Blood Analysis (FSH, LH, T, E) | • | | • (Only T) | • | • (Only T) | • | • (Only T) |
| Semen Analysis | • | • | | • | • | • | • |
| Drug dispensing | | • | | • | | | |

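### Section 4.2 gives two end points for dosing; if the 24-week one is followed, late week-26 hormone panels and the week-27 testosterone are taken off drug

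*Combined protocol and SAP*

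**What the plan says.** - **Length of dosing.** Section 4.2 says that "subjects will be provided with Natesto for the duration of the study (24 weeks treatment course"). The same sentence puts the study at 6 months; section 10.3 puts it at 27 weeks.
- **Start of dosing.** In the section 12 calendar, the row "Drug dispensing" is marked at Visit 2 (week 2) and Visit 4 (week 14) only. Section 7.4 adds testosterone draws "beginning one month after initiation of therapy", and the calendar has the first of these at week 6.
- **Sampling.** Section 7.4: "Follow-up visits will be conducted at week 14+/- 7 days and 26+/- 7 days". These visits carry the full FSH, LH, estrogen and testosterone panel. The calendar ends with "Visit 6 (Week 26) | Visit 7 (Week 27"), and Visit 7 includes a testosterone-only draw. Section 7.4 also says: "Additional semen analysis will be performed at weeks 15+/- 7 days and 27+/- 7 days".
- **Other androgens.** Section 7.3 tells patients to "refrain from using any other androgen replacement therapy option during the study".
- **Endpoint and analysis.** Section 10.1 sets the primary endpoint at six months of treatment. Section 3.1 names weeks 14 and 26 for the hormones. Section 10.4 analyses hormone levels across the whole study and does not say which draws are included.

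**The concern.** Counted from week 2, the two descriptions of dosing in 4.2 end a week apart, and the last primary hormone panel and the last testosterone draw fall in or beside that week. Because no quantity or last-dose day is stated, two coordinators could dose differently and both comply. Other androgens are barred, so a man who has finished his course is untreated when sampled.

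The hypothesis in section 1.3 is that testosterone rises while FSH and LH are not materially affected. In samples taken off drug, testosterone may have partly fallen, which works against the hypothesis, and LH and FSH may have partly recovered, which works towards it. The second direction matters more, because it would make the drug look kinder to the pituitary axis than it is. Week 26 is one of only two post-baseline LH/FSH panels. Without a recorded last-dose date, the analyst could not tell which six-month values were on treatment.

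**Working it through.** This is calendar arithmetic; no sample-size formula applies.

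**Inputs.** First dispensing at week 2 and second at week 14 (section 12); first additional testosterone one month after the start (7.4), scheduled at week 6 (12); course of 24 weeks (4.2); full panel at week 26 ± 7 days (3.1, 7.4); last testosterone at week 27 (12).

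**Start of dosing.** 6 − 4 = week 2, which agrees with the first dispensing visit.

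**The plan's own figure.** Week 2 to 14 is 12 weeks and week 14 to 26 is 12 weeks; 12 + 12 = 24. The stated course is reproduced and ends at 2 + 24 = week 26.

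**Drug for the whole study.** 27 − 2 = 25 weeks (175 days). If Visit 7 is a week late, 28 − 2 = 26 weeks (182 days). The 24-week course is 168 days.

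**Days after the last dose under the 24-week course**, as (visit week − 26) × 7 + window offset:

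| Sample | Earliest | Nominal | Latest |
|---|---|---|---|
| Visit 6 full panel | −7 | 0 | +7 |
| Visit 7 testosterone | 0* | +7 | +14* |

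*No window is stated for this draw. The starred figures assume that the ± 7 days given for the week-27 semen analysis also applies to it.

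At Visit 6, only panels drawn on days +1 to +7 are affected.

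**Share of the data.** Post-baseline testosterone is drawn at weeks 6, 14, 15, 26 and 27, so week 27 is 1 of 5 draws. Post-baseline LH/FSH is drawn at weeks 14 and 26, so week 26 is 1 of 2.

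**Sensitivity to the starting point.**
- Visit 2 has no stated window. If a man starts *d* days after week 2 and his visits stay on study weeks, his latest Visit 6 and his nominal Visit 7 both fall 7 − *d* days after the last dose. Neither is off drug once *d* ≥ 7.
- Section 3.2 can be read as counting visit weeks from the start of treatment. A 24-week course then leaves Visit 6 at (26 − 24) × 7 = 14 days off drug (7 to 21 with the window) and Visit 7 at (27 − 24) × 7 = 21 days off (14 to 28). This reading widens the gap.

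**Size of the hormone effect.** It cannot be derived. The documents give no offset time for Natesto. Their only washout figure is the 4 weeks required after earlier androgens (6.1, item 5), which is an eligibility rule and not a measure of how fast this drug's effect fades.

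**The case against.** The strongest reply is that the off-drug samples may never occur. The main clause of 4.2 promises drug for the whole study; the 24 weeks is a parenthesis in a loosely rounded sentence. Nothing instructs anyone to stop at day 168. Even on the 24-week reading, 12 + 12 weeks ends at week 26, the last time named in 3.1, so the panel is on drug at nominal timing. The week-27 testosterone is an additional draw outside the times in 3.1, and a fall there would be conservative for the testosterone claim. The LH/FSH effect of 1 to 7 days off drug is unknown, and the week-14 panel, on drug under either reading, could still show suppression.

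Most of this stands, and it limits the point. It does not remove it. A site that supplies the stated 24 weeks over the two scheduled dispensing visits runs out at week 26, so the harmful reading is a natural one. No text describes Visit 7 as an off-drug visit, and weeks 26 and 27 repeat the pattern of weeks 14 and 15, where both draws are on drug. Whether week 27 enters the primary hormone analysis is left open by 10.4. Uncertainty about the starting point helps late starters, but the alternative count from first dose makes the gap larger.

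**Conclusion.** The concern holds. Counted from week 2, the 24-week course ends one week before the last scheduled sample, so it conflicts with the promise of drug for the whole study. If the 24-week figure governs, week-26 panels drawn on days +1 to +7 and the week-27 testosterone (nominally day +7) are untreated samples in a study whose endpoint is hormone change on treatment.

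This rests on three assumptions: the first dose is taken at the week-2 dispensing, visits follow study weeks, and dosing stops at 24 weeks. If dosing continues to Visit 7 there is no bias. The number of men affected and the size of the hormone shift cannot be obtained from the documents. Nothing is claimed here about the semen results. The point should be corrected because the correction is easy and the affected data are primary, but it does not undermine the study as a whole.

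**What to change.** **Preferred.** Amend 4.2 to say that dosing continues until the last scheduled sample is drawn at Visit 7: 25 weeks from week 2, or up to 26 if Visit 7 is a week late. State the quantity dispensed. Thirteen weeks of drug at each of Visits 2 and 4, with unused drug kept, is enough: 2 + 13 = week 15, the latest Visit 4, and 15 + 13 = week 28, the latest Visit 7 if the ± 7 days applies. If visits are meant to be counted from first dose, say so; supply must then last 27 to 28 weeks.

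**Cost, counting from week 2.** One sentence and 7 to 14 more days of drug per man: 7/168 = 4.2% to 14/168 = 8.3%. At the three-times-daily dosing in 1.3 this is 21 to 42 doses per man, or 1,680 to 3,360 for the 80 men in 10.3 (840 to 1,680 for the 40 in 4.1). Each man has one to two weeks more exposure. If the drug budget already assumes supply to the last visit, the added cost is smaller or nil.

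**If 24 weeks is kept.** Set the Visit 6 window to −7 to 0 days from the last dose, or require the last dose to follow the Visit 6 draw. Take the six-month hormone endpoint from Visit 6 and report week-27 testosterone separately as post-treatment. The one-sided window needs no extra drug; it costs some scheduling freedom and gives 23 to 24 weeks of exposure at Visit 6. Holding the last dose until the draw needs up to 7 more days of drug for men seen late.

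**Either way.** Record each man's last-dose date, and keep men who stop early in the intention-to-treat analysis required by 5.3.
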